#### **2.3.3. Pharmacokinetics Evaluable Analysis Set**

PK evaluable analysis set includes all enrolled subjects who receive at least 1 dose of ibrutinib and have at least 1 available PK sample after treatment.

## **2.4. Study Day and Relative Day**

Study Day 1 or Day 1 refers to the start of the first study drug administration. All efficacy and safety assessments at all visits will be assigned a day relative to this date.

Study day or relative day for a visit is defined as:

- Visit date - (date of Study Day 1) +1, if visit date is  $\geq$  date of Study Day 1
- Visit date - Date of Day 1, if visit date  $<$  date of Study Day 1

There is no 'Day 0'.

## **2.5. Baseline**

Baseline is defined as the last observation prior to the start of the first study agent administration.

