## 4.2. Exclusion Criteria

Any potential subject who meets any of the following criteria will be excluded from participating in the study:

1. Involvement of the central nervous system by WM.
2. Evidence of disease transformation.
3. Prior exposure to ibrutinib or other BTK inhibitors.
4. Known hypersensitivity reaction (eg. Anaphylactic and anaphylactoid reactions) to ibrutinib or to the excipients in its formulation. Refer to the IB for a list of excipients.
5. Received any WM-related therapy (eg, chemotherapy, immunotherapy, investigational drug)  $\leq 30$  days prior to first administration of study treatment.
6. Received a prior allogeneic hematopoietic stem cell transplant.
7. Plasmapheresis  $< 35$  days prior to the initiation of study drug, except when at least one serum IgM central assessment was performed during the screening period and was  $> 35$  days from the most recent plasmapheresis procedure.
  - Subjects with high IgM values or viscosity symptoms during screening may receive plasmapheresis prior to initiating study drug (refer to Section 8.5) if the previous plasmapheresis was performed  $> 35$  days before the plasmapheresis performed during screening (in order to obtain a true baseline IgM value for efficacy evaluations).
8. History of other malignancies, except:
  - Malignancy treated with curative intent and with no known active disease present for  $\geq 2$  years before the first dose of study drug and felt to be at low risk for recurrence by treating physician.
  - Adequately treated non-melanoma skin cancer or lentigo maligna without evidence of disease.
  - Adequately treated carcinoma in situ without evidence of disease.
9. Vaccinated with live, attenuated vaccines within 4 weeks of first dose of study drug.
10. Infection requiring systemic treatment that was completed  $\leq 14$  days before the first dose of study drug.
11. Bleeding disorders (eg, von Willebrand's disease) or hemophilia.
12. Stroke or intracranial hemorrhage within 6 months prior to enrollment.

13. Infection with human immunodeficiency virus (HIV).
14. Active infection with hepatitis B or hepatitis C.

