### **8.5. Plasmapheresis**

Management of hyperviscosity in WM patients may include plasmapheresis before and during treatment with study drug. Modifications to the dosing of study drug are not required.

In the event that a subject requires plasmapheresis prior to study treatment, the IgM level obtained prior to plasmapheresis should be considered as the baseline value and study drug should be initiated shortly thereafter (not more than 7 days) after last plasmapheresis. IgM level obtained within five half-lives (ie,  $\leq 35$  days) after the last plasmapheresis should not be considered for response evaluation. An IgM level obtained more than 35 days after plasmapheresis can be used in response determination. The IgM level prior to and after each plasmapheresis during the screening phase and during the study should be collected centrally and will be recorded in the eCRF.

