### **9.1.3. Treatment Phase**

Details of the procedures performed during the treatment phase are outlined in the **TIME AND EVENTS SCHEDULE**. The latest measurements taken on Day 1 of Week 1 before administration of study drugs or at screening will be defined as the baseline values. Clinical evaluations and laboratory studies may be repeated more frequently, if clinically indicated. If a subject shows signs of progression on physical examination or laboratory assessment, a suspected PD visit should be scheduled and the subject may continue study treatment until progression is confirmed. If progressive disease is diagnosed, the subject will discontinue study drug, complete the EOT Visit and enter the Follow-up Phase.

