#### **9.2. Efficacy Evaluations**

Efficacy evaluations will be conducted as outlined in the [TIME AND EVENTS SCHEDULE](#). Response assessments will be performed using the modified consensus criteria adapted from the VIth IWWM (NCCN 2019) ([Attachment 1](#)).

Progression of nodal and extranodal disease should be evaluated based on the revised criteria for malignant lymphoma described in the revised International Working Group for NHL.

Efficacy evaluation will include the following components:

- Hematologic parameters by complete blood count (CBC)
- Quantitative IgM serum immunoglobulins

- Quantitative serum-M protein (serum protein electrophoresis [SPEP])
- Serum free light chain assay
- Qualitative serum immunofixation, if applicable
- Radiographic evaluation, if applicable
- Bone marrow aspirate and biopsy, if applicable

Sequential changes in IgM levels used for assessing responses can be determined either by SPEP or by quantitative IgM serum immunoglobulins. It is crucial that for each subject, sequential response assessments are performed using the same methodology which is prespecified by site.

In the event a subject required plasmapheresis prior study treatment, the IgM level obtained prior plasmapheresis will be considered as the baseline value and study treatment should be initiated shortly thereafter (not more than 7 days) after last plasmapheresis. IgM level obtained within five half-lives (ie,  $\leq 35$  days) after plasmapheresis should not be considered as nadir on therapy or for response evaluation. IgM levels obtained more than 35 days after plasmapheresis can be used in response determination.

Any suspected case of disease progression should be reported to the Sponsor within 24 hours of awareness. If disease progression is suspected solely based on the results of a single examination or a single laboratory parameter (eg, IgM), this finding should be confirmed by a subsequent evaluation at least within 4 weeks from the first finding. Additional hematologic parameters, radiographic evaluation and bone marrow aspirate and biopsy should be performed at the discretion of the treating physician to confirm progressive disease if indicated.

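### SAP 2.5 omits the Protocol's plasmapheresis exception for baseline IgM, so a subject exchanged during screening is reported with a post-exchange baseline (minor; no endpoint affected)

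*SAP*

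**What the plan says.** **SAP.** Section 2.5 reads: "Baseline is defined as the last observation prior to the start of the first study agent administration". It applies to all variables, and the word plasmapheresis does not occur in the SAP. Two planned outputs use a baseline IgM. Section 4.1 summarizes serum IgM among the baseline disease characteristics, and section 6.2 lists IgM among the laboratory tests reported as change from baseline.

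**Protocol, general rule.** Section 9.1.3: "The latest measurements taken on Day 1 of Week 1 before administration of study drugs or at screening will be defined as the baseline values".

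**Protocol, IgM rule.** For a subject exchanged before treatment, section 8.5 says "the IgM level obtained prior to plasmapheresis should be considered as the baseline value", and section 9.2 repeats this. Both sections also restrict IgM values from the 35 days after an exchange; in the words of 9.2 they "should not be considered as nadir on therapy or for response evaluation". Exclusion criterion 7 allows exchange during screening for high IgM or viscosity symptoms, provided that any previous exchange was more than 35 days earlier, "in order to obtain a true baseline IgM value for efficacy evaluations".

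**Protocol, timing and data.** Section 8.5 adds that "study drug should be initiated shortly thereafter (not more than 7 days) after last plasmapheresis", and "The IgM level prior to and after each plasmapheresis during the screening phase and during the study should be collected centrally", with entry in the eCRF. The Time and Events Schedule has quantitative immunoglobulins at Screening and at Week 1.

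**The concern.** The SAP carries over the Protocol's general baseline rule but not its specific rule for IgM. For a subject exchanged during screening the two rules pick different measurements, and the SAP picks one that the Protocol sets aside. One study report would then rest on two IgM baselines for the same subject: the pre-exchange value that the investigator uses to grade response, and a lower value in the tables. IgM is the main response variable in Attachment 1, so a reader comparing the IgM tables with the reported responses could meet a mismatch that nothing explains.

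Such subjects can be expected in principle. Inclusion criterion 6 admits symptomatic hyperviscosity, serum viscosity above 4.0 centipoises, and monoclonal protein above 6 g/dL.

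**Working it through.** **1. The plan's own figures.** With 17 subjects, a null rate of 0.32 and an assumed rate of 0.698, the exact 90% lower limit is 0.311 for 9 responders (fails) and 0.364 for 10 (passes). The rule is therefore 10 or more of 17. Its exact one-sided error is 0.0204 and its power 0.892, which meets the stated 0.05 and 85%. No input to this calculation is an IgM baseline.

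**2. Which value each rule selects.** Take a subject exchanged in screening.

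- The last exchange is 0 to 7 days before Day 1 (Protocol 8.5).
- IgM is taken before and after that exchange (8.5) and again at Week 1 (schedule).
- Protocol 8.5 and 9.2 select the pre-exchange value.
- SAP 2.5 selects the last value before dosing. That is a post-exchange value, 0 to 7 days old relative to the exchange and so well inside the 35-day window.

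**3. Size of the difference.** The documents give no exchange effect and no count of exchanged subjects. Assumptions:

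- pre-exchange IgM of 60 g/L;
- a fraction f of 20% to 60% removed;
- a deficit that closes with a 7-day half-life, since Protocol 8.5 equates five half-lives with 35 days (35 / 5 = 7);
- an on-treatment IgM of 27 g/L, for the change only.

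Formulas, for a sample t days after exchange:

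- deficit D = 60 × f × 0.5^(t/7)
- SAP baseline = 60 − D
- shift in the mean of 17 per affected subject = D / 17
- change from SAP baseline = 27 − (60 − D), against 27 − 60 = −33 g/L from the Protocol baseline

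| Removed | SAP baseline, t = 0 / 7 (g/L) | Shift in mean of 17, t = 0 / 7 (g/L) | Change at 27 g/L, t = 0 / 7 (g/L) |
|---|---|---|---|
| 20% | 48 / 54 | 0.71 / 0.35 | −21 / −27 |
| 40% | 36 / 48 | 1.41 / 0.71 | −9 / −21 |
| 50% | 30 / 45 | 1.76 / 0.88 | −3 / −18 |
| 60% | 24 / 42 | 2.12 / 1.06 | +3 / −15 |

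The range per affected subject is 6 / 17 = 0.35 to 36 / 17 = 2.12 g/L. The apparent rise of 3 g/L needs both 60% removal and a sample with no recovery.

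**4. Later visits.** At nominal timing Week 5 (Day 29) is 28 to 35 days after the last exchange, or 25 to 38 with the 3-day visit window. By the same half-life, 0.5^4 = 6% to 0.5^5 = 3% of the deficit remains at nominal timing. The discrepancy in SAP 6.2 therefore comes almost wholly from the baseline and hardly from the Week 5 value.

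**The case against.** **No endpoint depends on this.** A reader might infer that the response rate is computed from the wrong baseline, since a 50% fall from the pre-exchange value would show as only 37.5% against a baseline lowered by 20%, and as no fall at all against one lowered by 50%. The documents do not support that reading. ORR, CRR and the VGPR rate are investigator assessments under Protocol 8.5, 9.2 and Attachment 1, and the SAP does not re-derive response or progression from its own IgM baseline. This objection stands in full and keeps the point minor.

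**The Protocol has the same general rule.** SAP 2.5 matches Protocol 9.1.3, and a specific IgM rule can be read as overriding a general one, so the Protocol need not be called self-contradictory. That stands for the Protocol. It does not rescue the SAP, which contains only the general rule and points to no exception.

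**SAP 6.2 is a safety table.** A last-pre-dose baseline is usual there, and the Protocol ties its pre-exchange baseline and 35-day restriction to efficacy, nadir and response. This stands in part. It would go beyond the Protocol to remove the early values from the 6.2 summaries, but the table should still say which baseline it uses. SAP 4.1 describes disease burden and is not covered by this argument.

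**The illustration is assumed throughout.** It is, and recovery before Day 1 can halve the effect; the range above allows for that.

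**Conclusion.** The point holds as a minor one. SAP 2.5, as written, selects a baseline IgM that Protocol 8.5 and 9.2 rule out for any subject exchanged during screening. The direct consequence is an understated baseline serum IgM in SAP 4.1. The secondary one is an IgM change in SAP 6.2 measured from a different baseline than the investigator's response.

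Under the stated assumptions each affected subject lowers the mean baseline IgM of 17 by about 0.35 to 2.12 g/L. This presumes that IgM is summarized by a mean, since SAP 4.1 does not name the statistic for it. The number of affected subjects is unknown and may be zero; one would be about 6% of the set (1/17). ORR, CRR, VGPR rate, DOR, PFS, power and the decision rule are unchanged.

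**What to change.** Add to SAP 2.5:

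> For serum IgM in subjects who have plasmapheresis during screening, before first dose, baseline is the pre-plasmapheresis value as set out in Protocol 8.5 and 9.2.

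Apply it to the serum IgM summary in SAP 4.1. In the SAP 6.2 IgM table, add a footnote stating which baseline is used. In the listings, flag IgM values obtained within 35 days after a plasmapheresis, but keep them in the 6.2 summaries.

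Extending the rule to M-protein by SPEP is optional. Protocol 9.2 says "Sequential changes in IgM levels used for assessing responses can be determined either by SPEP or by quantitative IgM serum immunoglobulins", but Protocol 8.5 words the baseline rule, and requires sampling before and after exchange, only for IgM.

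The cost is one sentence, one footnote and one listing flag in a revised SAP. No new data are needed, because Protocol 8.5 already has IgM collected centrally around each exchange and entered in the eCRF. No Protocol change is needed. A cross-reference in Protocol 9.1.3 would be a drafting nicety, and under Protocol 17.1 it would take a formal amendment.

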## **2.6. Treatment Duration**

Treatment duration will be calculated from the date of the first dose of study drug to the date of the last dose of study drug, as follows:

Treatment Duration = date of last dose of study drug – date of first dose of study drug + 1 day.

## **2.7. Time on Study**

Time on study will be calculated from the first study drug administration date to the study exit date or the last known alive date if the subjects are still in the study, as follows:

Time on Study = study exit date/last known alive date – first study drug administration date + 1 day.

## **2.8. Dose Intensity**

The dose intensity (mg/day) of study drug is calculated as (sum of total daily dose during the treatment phase)/treatment duration.

## **2.9. Relative Dose Intensity**

Relative dose intensity (%) is defined as the percentage of total cumulative dose administered (mg) versus the total expected dose (mg). Total cumulative dose administered is the sum of daily dose taken over the whole study course; and total expected dose (mg) is the product of the duration of the treatment (day) and the assigned daily dose. Assigned daily dose is 420 mg, unless dose is modified due to the use of CYP3A inhibitor or study drug discontinuation. Relative dose intensity is calculated by total cumulative dose administered / total expected dose  $\times 100\%$ .

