  - Note: If Hepatitis B surface antigen (HBsAg) is positive, the subject is excluded. Hepatitis B DNA polymerase chain reaction (PCR) needs to be confirmed negative prior to first study agent administration in subjects who are Hepatitis B core antibody positive. If Hepatitis C antibody is positive, RNA PCR needs to be performed and confirmed negative prior to the first study agent administration. Patient with history of Hepatitis C virus infection should have documented 24wks of sustained virologic response (SVR) in order to be eligible for the study.
15. Major surgery (as defined in Section [8.4.2](#)) within 4 weeks of first dose of study drug.
16. Any life-threatening illness, medical condition, or organ system dysfunction that, in the investigator's opinion, could compromise the subject's safety or put the study outcomes at undue risk.
17. Currently active, clinically significant hepatic impairment Child-Pugh Class B or C according to the Child Pugh classification (see [Attachment 4](#)).
18. Currently active, clinically significant cardiovascular disease, such as uncontrolled arrhythmia or Class 3 or 4 congestive heart failure as defined by the New York Heart Association Functional Classification ([Attachment 7](#)); or a history of myocardial infarction, unstable angina, or acute coronary syndrome within 6 months prior to first dose.
19. Requires or receiving anticoagulation with warfarin or other Vitamin K antagonists (eg, phenprocoumon).
20. Unable to swallow capsules or malabsorption syndrome, disease significantly affecting gastrointestinal function, or resection of the stomach or small bowel, symptomatic inflammatory bowel disease or ulcerative colitis, or partial or complete bowel obstruction.
21. Requires treatment with a strong cytochrome P450 (CYP) 3A inhibitor (see [Attachment 3](#)).
22. Lactating or pregnant.
23. Unable to understand the purpose and risks of the study and to provide a signed and dated informed consent form (ICF) and authorization to use protected health information (in accordance with national and local subject privacy regulations).

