#### **6. DOSAGE AND ADMINISTRATION**

Ibrutinib will be administered orally, once daily, at a dose of 420 mg (140 mg × 3 capsules taken together at one time). Protocol-specified dose modifications of ibrutinib will be made as

necessary. Study drug (3 capsules) is administered orally once daily with approximately 8 ounces (240 mL) of water. The capsules should be swallowed whole and should not be opened, broken, or chewed. The use of strong CYP3A inhibitors/inducers, and grapefruit and Seville oranges should be avoided for the duration of the study (Section 8.2 and Attachment 3).

If a dose is not taken at the scheduled time, it can be taken as soon as possible on the same day with a return to the normal schedule the following day. The subject should not take extra capsules to make up the missed dose. Missed doses of study drug will not be made up.

The first dose will be administered in the clinic on Day 1 of Week 1, after which study drug will be self-administered daily by the subjects on an outpatient basis. Study drug will be dispensed to subjects in bottles. Unused study drug dispensed during previous visits must be returned to the site and drug accountability records (Section 14.5) updated at each visit. Returned capsules must not be re-dispensed to anyone.

Study drug dosing is continuous (without interruptions) throughout the Treatment Phase.

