## **6.5. Dose Modification for Hepatic Impaired Subjects**

Ibrutinib is metabolized in the liver. For subjects with mild liver impairment (Child-Pugh class A), the recommended dose for ibrutinib is 140 mg daily (one capsule). Subjects with moderate or severe hepatic impairment (Child-Pugh class B or C) should avoid using ibrutinib. Monitor subjects for signs of toxicity and follow dose modification guidance as needed.

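### The SAP's relative dose intensity adjusts the expected dose for CYP3A inhibitors but not for the Child-Pugh A dose in Protocol 6.5

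*SAP*

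**What the plan says.** SAP 2.9 defines RDI as dose taken over dose expected, in percent. On the denominator it says that "total expected dose (mg) is the product of the duration of the treatment (day) and the assigned daily dose", and then: "Assigned daily dose is 420 mg, unless dose is modified due to the use of CYP3A inhibitor or study drug discontinuation". Hepatic impairment is not among the exceptions, and no other SAP section supplies a different expected dose. SAP 4.3 reports RDI in the extent-of-exposure summary on the safety set, with mean, SD, median, minimum and maximum.

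The protocol's general dose is 420 mg once daily (Section 6), and the same section allows for modifications that the protocol specifies. These are of three kinds:

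- Toxicity reductions to 280 mg and then 140 mg (Section 6.4, Table 2).
- Changes for CYP3A inhibitors (Section 8.2.1 and Attachment 5).
- Hepatic impairment (Section 6.5): "For subjects with mild liver impairment (Child-Pugh class A), the recommended dose for ibrutinib is 140 mg daily (one capsule".

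On eligibility, Protocol 4.2 excludes "Currently active, clinically significant hepatic impairment Child-Pugh Class B or C". Class A is not excluded.

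**The concern.** SAP 2.9 does not simply measure every subject against 420 mg. It changes the reference when the dose is altered for a CYP3A inhibitor, a reason unrelated to how the subject tolerated the drug. The Section 6.5 dose is the same kind of case, yet it is still compared with 420 mg. A class A subject who takes every Section 6.5 dose therefore gets the same RDI as a subject on the 420 mg regimen who takes one third of it.

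The trial plans about 17 subjects and is meant to support full approval in China. In an exposure table of that size, one or two such subjects can set the reported minimum and visibly move the mean. Baseline liver function in SAP Table 1 is classified by NCI criteria rather than Child-Pugh, so that table would not show a reader which subjects Section 6.5 covers.

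**Working it through.** The documents give no RDI figure to reproduce. The check applies the SAP formula directly.

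**Inputs**
- General dose: 420 mg/day (Protocol 6; SAP 2.9).
- Class A dose as stated: 140 mg/day (Protocol 6.5).
- Dose with a moderate CYP3A inhibitor: 280 mg/day (Protocol 8.2.1, Attachment 5).
- Treatment duration: D days (SAP 2.6).
- Planned number of subjects: 17 (SAP 1.2), used only to size the effect on the mean.

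**Can a class A subject be eligible?** Under Attachment 4, albumin in the 28-35 g/L band with the other four measures at 1 point scores 2 + 4 × 1 = 6, which is class A. The inclusion limits on AST/ALT, bilirubin and coagulation (Protocol 4.1, criterion 7) do not rule this out.

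**Step 1. One subject, constant dose, no missed days.** RDI = (daily dose taken × D) / (assigned daily dose × D) × 100%, so D cancels. The first row takes the natural reading that a CYP3A-modified dose becomes the assigned dose.

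| Subject | Taken (mg/day) | Assigned under SAP 2.9 (mg/day) | RDI |
|---|---|---|---|
| Moderate CYP3A inhibitor throughout | 280 | 280 | 280/280 = 100% |
| Section 6.5 dose from Day 1 | 140 | 420 | 140/420 = 33.3% |

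With the Section 6.5 dose in the denominator, the second subject scores 140/140 = 100%.

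**Step 2. Section 6.5 dose starting later.** Let f be the share of treatment time first spent at 420 mg (assumed values). Under SAP 2.9, RDI = (f × 420 + (1 − f) × 140) / 420.
- f = 25%: (105 + 105)/420 = 50.0%
- f = 50%: (210 + 70)/420 = 66.7%
- f = 75%: (315 + 35)/420 = 83.3%

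**Step 3. Effect on the summary.** Each subject of the Step 1 kind lowers the mean of 17 by (100 − 33.3)/17 = 3.9 points, whatever the others score. The number k of such subjects is an assumption.

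| k of 17 | Fall in mean RDI (points) | Mean if all others score 100% |
|---|---|---|
| 0 | 0 | 100% |
| 1 | 3.9 | 96.1% |
| 2 | 7.8 | 92.2% |

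For k of 1 or 2 the minimum could be 33%. The median of 17 is the ninth ordered value, and each such subject shifts it by at most one rank, so it would move little.

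**The case against.** The strongest objection is that a fixed reference is a legitimate choice. SAP 2.9 defines RDI only as dose taken against dose expected and does not present it as a compliance measure. A class A subject on 140 mg does receive one third of the study's general dose, and 33% says so truthfully. A reader might infer that the table would report under-dosing that did not happen. The SAP does not support that, because it nowhere equates a low RDI with non-compliance. This part of the objection stands. What it leaves is an inconsistency: the SAP gives up the fixed reference for one non-toxicity dose and keeps it for the other.

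A reader might also infer that any dose the protocol directs belongs in the denominator. That goes too far. Table 2 reductions are protocol-directed as well, and SAP 2.9 measures them against 420 mg. The line that fits the SAP's own rule is between toxicity and non-toxicity reasons.

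Other outputs limit a misreading. SAP 4.3 also gives dose intensity in mg/day, cumulative dose, and the number of subjects with dose modifications, with reasons. This stands in part. SAP 4.3 describes modification as skipped or reduced doses, so a subject who starts at 140 mg might not be counted there.

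Finally, the effect may never arise. The documents do not say how many class A subjects to expect. That is correct, and the sizes above are conditional on it.

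**Conclusion.** The point holds as a small inconsistency in a descriptive measure. SAP 2.9 resets the assigned daily dose for CYP3A inhibitor use but not for the Section 6.5 dose, although subjects to whom Section 6.5 applies are eligible.

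The 33.3% is conditional: it needs an enrolled class A subject on 140 mg from the first dose with no missed doses. A reader might take it to apply to every class A subject, but the result is 50% to 83% if 25% to 75% of treatment time was first spent at 420 mg. The falls of 3.9 and 7.8 points in the mean assume one or two such subjects among 17. With none, nothing changes.

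A reader might also infer that the efficacy result is at risk. It is not. SAP 5.2.2 compares the exact lower confidence limit for ORR with 0.32 in all treated subjects, and RDI enters neither that comparison, nor the secondary endpoints, nor any analysis-set definition. Improving this is worthwhile but not essential. No view is taken on which dose is right; the two passages need to be reconciled.

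**What to change.** Reconcile SAP 2.9 with Protocol 6.5. In the assigned-daily-dose sentence, add dosing recorded as due to hepatic impairment under Protocol 6.5 to the listed exceptions, alongside CYP3A inhibitor use. State that Table 2 toxicity reductions remain measured against 420 mg, so that the change does not absorb them.

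Identify these subjects from the recorded reason for the dose, not from Child-Pugh scores followed over time. INR is scheduled only at Screening, Week 17 and End of Treatment, so a running score could not be kept up. The class alone would not separate them either: a subject with all five measures at 1 point scores 5 and is also class A under Attachment 4.

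The cost is one phrase in the SAP and a matching line in the exposure programming. Check beforehand that a reason is captured for a subject who starts below 420 mg, since the documents do not show the case report form. No new assessments or changes to the efficacy analysis are needed.
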